6.1.1. Selection and Timing of Doses

For patients randomly assigned to LY3209590, an initial dose will be determined using Table 1 for Algorithm 1 (see Section 10.8). The weekly dose adjustment thereafter will be based on guidance provided in Section 10.8. The doses will be administered at approximately the same time and day each week.

If a patient misses a scheduled dose of LY3209590, it should be administered as soon as possible, but no later than 3 days after the scheduled administration. If more than 3 days have elapsed since the scheduled administration, the dose should be skipped and the next injection will occur at the next scheduled day and time.

Insulin degludec should be administered at the same time each day adjusted per the modified Riddle algorithm (Section 10.8.2).

Patients who miss a dose of insulin degludec should inject their daily dose during waking hours upon discovering the missed dose. Instruct patients to ensure that at least 8 hours have elapsed between consecutive insulin degludec injections (Tresiba® USPI).

The actual date, time and dose of each dose administrations (LY3209590 and insulin degludec) will be recorded in the participant's diary (and participant's medical record when administered at the site).

For details on the titration algorithms to be used, refer to Section 10.8.

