6.7.1. Treatment after Study Completion

The last study treatment administration for patients treated with LY3209590 will be at Week 25 and for patients treated with insulin degludec the evening before the last study visit at Week 26. The washout of LY3209590 may take up to 10 weeks to complete. Any appropriate antihyperglycemic treatment must therefore be instituted slowly and under regular supervision of blood glucose profiles after discontinuation of LY3209590. If another basal insulin is used as a replacement for LY3209590 or insulin degludec, insulin therapy will be instituted using the Riddle algorithm as needed based on FG (Section 10.8). Since CCI

Therefore, a slow up-titration of another basal insulin is necessary to prevent hypoglycemia due to overlapping insulin action. For example, no insulin would be required until the study participant's blood glucose increases to >100 mg/dL, and then daily basal insulin would be initiated and adjusted based on FG.

Study participants assigned to the insulin degludec treatment group will switch to another glucose lowering regimen per investigator guidance after the last study treatment administration. If they switch to an insulin treatment and insulin degludec is chosen, they can continue with the same dose used until Visit 20 of the study. If they switch to another basal insulin (e.g., insulin glargine), study participants should inject a daily dose, which is 20% lower than the last dose of insulin degludec used before Visit 20 and titrate under supervision of the investigator using the country-specific label for their pre-study basal insulin.

7. Discontinuation of Study Intervention and Participant Discontinuation/Withdrawal

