7.1.2. Temporary Discontinuation

In certain situations after randomization, the investigator may need to temporarily discontinue (interrupt) IP (for example, due to an AE or a clinically significant laboratory value). The maximum time allowed for a temporary interruption of IP is 14 days. If IP interruption is due to an AE, the event is to be documented and followed according to the procedures in Section 8.3 of this protocol. Investigators should inform the sponsor that IP has been temporarily interrupted. Every effort should be made by the investigator to maintain patients on IP and to restart IP after any temporary interruption, as soon as it is safe to do so. The data related to temporary interruption of IP will be documented in source documents and entered in the eCRF.

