9.4.1. General Considerations

Unless otherwise stated, the efficacy analyses will be conducted on efficacy analyses set (EAS) based on the Efficacy Population using the data up to the study treatment discontinuation (defined as the observed data with collection date before or at the last dose date +10 days). Sensitivity analyses for selected efficacy measures may be conducted on the Randomized Population using the data up to the study treatment discontinuation.

Unless otherwise stated, the safety analyses except for hypoglycemia will be conducted on the safety analyses set based on the Safety Population using all data collected during the study including treatment and follow-up period regardless of the treatment disposition status. The details for analyses on hypoglycemia will be documented in the SAP.

Unless otherwise specified, the baseline value used for the analyses will be the last non-missing value obtained for each participant prior to or on the date of first study IP dose (or randomization visit date if first dose date is missing). The baseline liver enzyme lab measures will be the average of all assessments prior to and at randomization visit.

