the observed data with collection date before or on the last dose date +10 days). Sensitivity analyses for selected efficacy measures may be conducted on the Randomized Population using the data up to the study treatment discontinuation.

Unless otherwise stated, the safety analyses will be conducted on the safety analyses set based on the Safety Population using all data collected during the study including treatment and follow-up periods regardless of the treatment disposition status. The safety measures will be summarized and compared between LY3209590 (by pooling LY3209590 Algorithm 1 and LY3209590 Algorithm 2 data) and insulin degludec. Safety parameters derived from FGM measures will be summarized and compared between LY3209590 Algorithm 1 and insulin degludec.

Unless otherwise specified, the baseline value used for the analyses will be the last non-missing value obtained for each participant prior to or on the date of first study IP dose (or randomization visit date if first dose date is missing). The baseline liver enzyme lab measures will be the average of all assessments prior to and at randomization visit.

All tests of treatment effects will be conducted at a 2-sided alpha level of 0.1, unless otherwise stated, and all confidence intervals (CIs) will be given at a 2-sided 90% level.

Puerto Rico and the United States (US) are always pooled in the analysis, as Puerto Rico will be considered part of US during randomization. All analyses using country in the model will use pooled country, unless otherwise specified. No other pooling of countries is needed.

For continuous measurements, summary statistics will include sample size, mean, median, standard deviation (SD), minimum, and maximum. For certain variables that are considered to be log-normally distributed, the geometric mean and coefficient of variation (CV) will be provided instead.

For categorical measurements, summary statistics will include sample size, frequency, and percentage. Fisher's exact test will be used. Chi-squared test will be used for multi-category variables.

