5.10.1. Study Drug Exposure

Exposure in days in the study will be calculated for each patient and summarized by treatment group. Exposure during the treatment period will be calculated from date of first study basal insulin dose collected in the electronic case report form (eCRF) to date of discontinuation from study treatment (i.e., the last dose date for insulin degludec, and the last dose date + 7 days for LY3209590). The sum of exposure in total patient years will also be provided.

Frequency of subjects falling into the following different exposure ranges will also be summarized: >0 days, ≥ 7 days, ≥ 14 days, ≥ 30 days (1 month), ≥ 60 days (2 months), ≥ 90 days (3 months), ≥ 120 days (4 months), ≥ 183 days (6 months) days.

In addition, the duration of follow-up in days for each individual patient is calculated from the date of last dose of study drug for insulin degludec or the date of last dose of study drug + 7 days for LY3209590 to the last study visit date. The duration of the follow-up in days will be summarized (n, mean, standard deviation, minimum, maximum, median, and sum in total patient years) by treatment group.

The duration on study from date of the first study drug to the last study visit date (including the follow-up visit) will also be summarized by treatment group, the following summary statistics will be provided: n, mean, standard deviation, minimum, maximum, median, and sum in total patient years.

A by-patient listing of drug exposure data will be created to provide data for the CSR.

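### The common cut-off of last dose +10 days, applied as written, usually drops the primary Week 26 HbA1c of an LY3209590 patient who skips only the Week 25 dose, but keeps it after up to nine missed final degludec doses

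*SAP*

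**What the plan says.** SAP 5.1 bases the efficacy analyses on data up to study treatment discontinuation and defines that as "the observed data with collection date before or on the last dose date +10 days". Protocol 9.4.1 has the same definition: "the observed data with collection date before or at the last dose date +10 days". Neither text gives an arm-specific lag or an exception for a skipped dose.

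The dosing and visit rules that interact with it are these:

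- Protocol 6.7.1, final weekly dose: "The last study treatment administration for patients treated with LY3209590 will be at Week 25". The same section puts the final degludec dose one evening ahead of Visit 20.
- Schedule of Activities: Visit 19 (Week 24) and Visit 20 (Week 26) each have a window of ±3 days.
- Protocol 6.1.1, late LY3209590 doses: "If more than 3 days have elapsed since the scheduled administration, the dose should be skipped".
- Protocol 7.1.2, interruptions: "The maximum time allowed for a temporary interruption of IP is 14 days". These are treated separately from permanent discontinuation (7.1.1).
- Protocol 9.4.3: the intercurrent events of the primary estimand are stopping study medication and using rescue medication.
- SAP 5.7: the primary MMRM uses HbA1c at Weeks 6, 12, 16 and 26 and handles missing values under missing at random.
- SAP 5.10.1, for exposure only: treatment ends at "the last dose date for insulin degludec, and the last dose date + 7 days for LY3209590".

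**The concern.** One fixed number of days is applied to a weekly and a daily drug. Ten days leaves 10 − 7 = 3 days beyond the LY3209590 dosing interval, but 10 − 1 = 9 days beyond the degludec interval. A skip that the protocol itself directs can therefore turn a continuing LY3209590 patient's primary value into missing data, while a longer lapse in the degludec arm leaves the value in place.

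The event is plausible. Protocol 4.1.1 allows home self-injection from Week 13 to Week 25 outside titration visits, and Week 25 is not a titration visit. Nor is a patient 14 days after a dose clearly off drug, since Protocol 6.7.1 puts LY3209590 washout at up to 10 weeks.

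At stake is whether the data rule behind the non-inferiority decision matches the estimand and treats the arms alike. For an affected patient the last HbA1c in the primary model is Week 16, and Week 26 is inferred from the model although it was measured.

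**Working it through.** **Plan's own figure.** Protocol 9.2 states more than 80% power with 100 completers per arm, SD 1.1, margin 0.4, true difference 0 and two-sided alpha 0.1 (one-sided 0.05).

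- SE = 1.1 × √(1/100 + 1/100) = 0.1556
- Power = Φ(0.4/0.1556 − 1.645) = Φ(0.926) = 82.3% (82.1% with the noncentral t)

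The stated power is reproduced.

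**Gap from last dose to Visit 20.** Nominal days are Week 24 = 168, Week 25 = 175 and Week 26 = 182. Let v be the shift of Visit 20 and L the shift of the last dose from its nominal day. The value is kept if the gap is at most 10 days.

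| Situation | Formula | Gap (days) | Result |
|---|---|---|---|
| LY3209590, Week 25 dose on its nominal day | 7 + v | 4 to 10 | kept |
| LY3209590, only Week 25 skipped, Week 24 dose on its nominal day | 14 + v | 11 to 17 | removed |
| LY3209590, only Week 25 skipped, Week 24 dose also moved ±3 | 14 + v − L | 8 to 20 | removed in 43 of 49 whole-day combinations |
| Degludec, last dose missed | k + 1, k = 1 | 2 | kept |
| Degludec, last 7 doses missed | k + 1, k = 7 | 8 | kept |
| Degludec, last 9 doses missed | k + 1, k = 9 | 10 | kept |
| Degludec, last 10 doses missed | k + 1, k = 10 | 11 | removed |
| Degludec, last dose on Day 168 | 14 + v | 11 to 17 | removed |

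The 43 of 49 is a count of combinations, not a probability. The six that are kept need a late Week 24 dose together with an early Visit 20, with a combined shift of at least 4 days.

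**Fully dosed LY3209590 patients.** If the Week 25 dose is given early, the gap is 7 + v − L with L negative. One day early with Visit 20 three days late gives 7 + 3 + 1 = 11. Three days early with Visit 20 one to three days late gives 11 to 13. These values are removed with no dose missed. A degludec patient dosing daily up to the visit stays at 1 day. Window extensions under Protocol Appendix 10 are not counted here.

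**Effect on power.** The skip rate is not given, so the loss is assumed. With n = 100 for degludec and 100(1 − p) for LY3209590, complete-case power is:

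| Assumed loss p | Power |
|---|---|
| 0 | 82.3% |
| 1% | 82.1% |
| 2% | 81.9% |
| 5% | 81.4% |
| 10% | 80.5% |

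For p = 10%: SE = 1.1 × √(1/100 + 1/90) = 0.1598, and Φ(0.4/0.1598 − 1.645) = Φ(0.858) = 80.5%. This ignores the earlier visits and the baseline covariate in the MMRM.

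**The case against.** The best defence is that the cut-off defines data up to treatment discontinuation. SAP 5.7 attributes missing values to early discontinuation, and Protocol 7.1.2 keeps interruption apart from permanent discontinuation. On that reading a patient who skips one dose has not discontinued and is not touched. This reading is possible, and may be what the sponsor intends. But neither document says so: the parenthesis defines the retained data by collection date relative to last dose alone, and a programmer following it would drop the value.

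Three further points stand. The supportive estimand in SAP 5.7 uses all Week 26 data regardless of treatment status, so the value is analysed there, although non-inferiority is declared on the primary estimand. The different lag in SAP 5.10.1 serves exposure reporting and does not contradict 5.1; it shows only that the dosing intervals were recognised as different. And the Schedule of Activities places Visit 20 about one week after the last LY3209590 dose, so losses among fully dosed patients should be uncommon.

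A reader might go further and infer that the rule discards every such LY3209590 value, never discards a degludec value, or loses data in one arm only. The table rules this out: some skippers are kept, and degludec values go from ten missed doses onward or with an equal last-dose date. A degludec interruption covering the 14 days before Visit 20 gives a gap of 15 days and is also removed.

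A reader might also infer a bias toward LY3209590. The documents do not support a direction. A dose forgotten by a poorly adherent patient and one withheld after hypoglycemia could push the discarded values opposite ways.

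**Conclusion.** The point holds as a mismatch between a data rule and its estimand, with unequal reach in the two arms. Applied literally, the cut-off usually removes the Week 26 HbA1c of a continuing LY3209590 patient who skips only the last dose. It tolerates up to nine missed final degludec doses. It can also remove a fully dosed LY3209590 patient when the last dose is early and the visit late.

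The likely size is modest. Only the Week 26 value is lost, power stays above 80% even at an assumed 10% loss, and no bias estimate can be justified from the documents. The conclusion rests on the literal reading of the definition and on the nominal schedule with its stated windows. It merits correction because it concerns the primary endpoint and the present text leaves its handling to interpretation.

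**What to change.** State in SAP 5.1 and 5.7 that the cut-off of last dose +10 days applies only to participants recorded as having permanently discontinued study treatment. State also that the Week 26 values of all other participants enter the primary MMRM, subject to the existing rescue-medication rule. Note it as a clarification of Protocol 9.4.1.

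An arm-specific window built on SAP 5.10.1, giving 7 + 10 = 17 days for LY3209590, is not needed. For true discontinuers it would admit more data after stopping, under an estimand that asks what would happen had participants adhered.

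The cost is SAP wording and one dataset derivation from the treatment-disposition record; no new data are needed.

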5.2. Patient Disposition

All randomized participants who discontinue the study/treatment will be identified, and a reason for their discontinuation will be given. The reasons for study/treatment discontinuations will be summarized by treatment using the Randomized Population and the Efficacy Population.

Comparisons will be conducted using the Fisher's exact test. A listing of the primary reasons for study/treatment discontinuations will be generated for the Enrolled Population.

Reasons for discontinuation prior to randomization will also be summarized. A listing of the randomized treatments for this study will be provided.

5.3. Patient Characteristics

Demographic and baseline characteristics including but not limited to age (years), age groups (<65 years, ≥65 years and <75 years, ≥75 years), sex, ethnicity, race, country, region, weight (kg), body mass index (BMI: kg/m²), BMI groups (<25, ≥25 and <30, ≥30 and <35, and ≥35 kg/m²), eGFR groups (estimated glomerular filtration rate based on the modified Modification of Diet in Renal Disease [MDRD] equation: ≥90, <90 and ≥60, <60 and ≥30, and <30 mL/min/1.73 m²), duration of diabetes (years), baseline substance use (alcohol, drug, tobacco and caffeine baseline use status), baseline systolic blood pressure, baseline diastolic blood pressure, baseline HbA1c (% and mmol/mol), baseline HbA1c groups (<8.5%, ≥8.5%), fasting serum glucose (FSG: mmol/L and mg/dL), HbA1c screening group (HbA1c, <8.5% and ≥8.5% at Visit 1), DPP4 use, SGLT2 use and combination of OAM use will be summarized by treatment group for the Randomized Population, the Efficacy Population, and the Safety Population.

Comparisons of categorical variables between treatment groups will be assessed using a Pearson Chi-Square test. Comparisons of continuous variables between the treatment groups will be performed using a 1-way analysis of variance with treatment as the fixed effect. The by-patient listing of demographic and selected baseline characteristics will be provided for all randomized patients.

Number of randomized patients and number of randomized patients discontinued per investigator within country for each treatment group will be summarized. In addition, number of enrolled patients per investigator within each country will also be summarized.

5.4. Concomitant Medications

Concomitant medications used during the treatment period will be summarized by treatment groups and will be compared between treatment groups using Fisher's exact test for the Safety Population. The percentages of patients who took concomitant medication will be summarized by treatment using Preferred Terms (PTs) nested within Anatomical Therapeutic Chemical (ATC) Level 3 codes. The concomitant medications will be ordered by decreasing frequency within each ATC level.

5.5. Treatment Adherence

Treatment adherence will be summarized using the EAS. For a given study participant, overall adherence for treatment period is based on the ratio of the total number of doses taken to the total number of required doses. CCI

Adherence to the dosing algorithm is required from Visit 3 (Randomization) up to Visit 20. The number and percentage of investigator prescribed doses that did not follow the algorithm recommended dose and the number and percentage of patient actual administration dose that did not follow the investigator prescribed dose will be provided.

Similar descriptive statistics will be provided for patients randomized to LY3209590 Algorithm 2 arm and took at least 1 study dose.

5.6. Protocol Deviations

Important protocol deviations (IPDs) defined as deviations from the study protocol that may compromise the data integrity and patients' safety will be summarized by treatment group for the Randomized Population and the Efficacy Population. The listing of IPDs for the Randomized Population will also be provided.

5.7. Primary Outcome and Methodology

The primary objective is to compare the HbA1c change from baseline to Week 26 between LY3209590 and insulin degludec and will be based on the primary estimand described below.

The primary estimand is the treatment differences in the change in HbA1c from baseline to 26 weeks for the targeted study population if all patients would adhere to the treatment without intercurrent events. The analysis data will include data up to the discontinuation of study treatment for the Efficacy Population with baseline and at least one non-missing postbaseline measurement. There may be missing values due to the early discontinuation of study treatment. The MMRM model will be used with the HbA1c changes at Week 6, 12, 16 and 26 (the primary endpoint) and the missing values will be imputed implicitly in the MMRM analysis under the assumption of missing at random. The MMRM model will include treatment (LY3209590 Algorithm 1, insulin degludec), strata (country, DPPIV [yes/no], SGLT2 [yes/no] and baseline BMI [<30 , ≥ 30]), visit, and treatment by visit interaction and the baseline value of the dependent

variable as the fixed effects. The HbA1c is reported in unit of % and will be converted to the unit of mmol/mol using the following formula: HbA1c in mmol/mol = 10.93*HbA1c in % - 23.5 (<http://www.ngsp.org/ifccngsp.asp>). HbA1c analysis will be conducted based on both units.

In the MMRM model, the within-patient errors are modeled as an unstructured variance-covariance matrix. If the analysis fails to converge, the following variance-covariance matrix will be used (in order) until one converges:

1. Toeplitz with heterogeneity
2. autoregressive with heterogeneity
3. compound symmetry with heterogeneous variances
4. Toeplitz
5. autoregressive
6. compound symmetry without heterogeneous variances

The Kenward-Roger approximation will be used to estimate denominator degrees of freedom for the MMRM models. The following is an example SAS code:

```
proc mixed data=DATA;  
  class TREATMENT STRATIFICATIONS VISIT PATIENT;  
  model HbA1c=BASELINE TREATMENT STRATIFICATIONS VISIT  
        VISIT*TREATMENT / solution ddfm=kr;  
  repeated VISIT / subject=PATIENT type=un;  
  lsmeans TREATMENT*VISIT/ pdiff cl alpha=0.1 om=DATA;  
run;
```

The 2-sided 90% CI of the LS mean for individual treatment groups, treatment LS mean difference (LY3209590 Algorithm 1 versus insulin degludec) in the HbA1c change from baseline to Week 26 will be estimated. Similar analysis based on the above MMRM model will also be provided for the comparison between LY3209590 (by pooling LY3209590 Algorithm 1 and LY3209590 Algorithm 2) and insulin degludec.

With the primary estimand, LY3209590 Algorithm 1 will be declared noninferior to insulin degludec if the upper limit of the 2-sided 90% CI for the LS mean difference in the HbA1c change from baseline is below +0.4%.

A supportive estimand is the treatment differences in HbA1c change from baseline to Week 26 for the targeted study population regardless of the use of rescue medication or taking study medication. The analysis data will include all available data at Week 26 regardless of treatment disposition status for all randomized patients who took at least one dose of study treatment and have non-missing baseline. There will be missing endpoint due to early study discontinuation. The missing endpoint will be imputed by “return to baseline” imputation. Multiple imputations will be conducted and an analysis of covariance model including factors of treatment, country, DPPIV [yes/no], SGLT2 [yes/no], baseline BMI [<30 , ≥ 30], and baseline HbA1c as covariates will be performed by imputation data set. Then, the inference will be based on the bootstrap method.

